## **1. Study Protocol**

### **Hypothesis and Objectives**

The primary objective of this study is to investigate the effectiveness of the addition of a written action plan (WAP) on patient understanding and management of HS.

Hypothesis 1: Subjects randomized to the intervention group will self-report increased understanding of their HS and management plan, as compared to the verbal consultation (VC).

The secondary objective is to investigate the patients' comfort level in following their individualized WAPs at home.

Hypothesis 2: Subjects receiving a WAP will self-report increased comfort level in managing their HS at home with guidance from a WAP.

The tertiary objective is to investigate whether patients randomized to the control group prefer VC alone, WAP alone, both VC and WAP combined, or neither the VC nor the WAP.

Hypothesis 3: Subjects randomized to the control group will prefer their providers to use a combination of VC and WAP during their office visits.

The quaternary objective is to investigate the patients' anxiety level in managing their HS at home.

Hypothesis 4: Subjects receiving a WAP will self-report lower levels of anxiety in managing their HS at home.

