### **Study Design and Procedures**

Patient recruitment will take place during a routine dermatology. If the HS patient meets the inclusion criteria, he/she will be approached by a study coordinator about this study. If he/she agrees, he/she will sign an informed consent form.

Subjects will then be randomized to one of two groups:

- A control group – VC alone
- An intervention group – VC with WAP

In order to randomize subjects, randomization lists, which are concealed to all parties involved in this study, will be created using a computer software program. As each subject is enrolled, they will be assigned a subject number. After assignment of a subject number, the investigators will refer to the computer-generated randomization scheme corresponding to the assigned subject number to complete the randomization process.

After group assignment, the study coordinator will administer Survey A which will take approximately 10 minutes to both groups. All subjects will be asked to refrain

from asking any questions regarding HS or its treatment until the end of the office visit to ensure controlled delivery of information to all subjects.

The principal investigator will then conduct a routine office visit for the HS patients, consisting of an introduction, history taking, and assignment of Hurley stage. Next, the subjects in the control and intervention groups will receive an individualized VC and VC+WAP, respectively. Subjects from both groups will then complete Survey B which will take approximately 10 minutes. At the completion of Survey B, subjects in the interventional group will have completed the study. Those in the control group will then receive a VC+WAP, followed by completion of Survey C which will take approximately 10 minutes. This is to ensure that all subjects receive the same caliber of care. All Surveys and WAP documents that will be used in our study of written action plans in hidradenitis suppurativa are a standard of care intervention.

Information collected into the medical record during the routine office visit (specifically duration of disease, tobacco use, and disease severity) will be used for this research.

Both groups will take Survey D at a routine follow up visit. Survey D (which will take approximately 10 minutes) is to evaluate if the action plan has had any long-term impact or if it results in behavior change.

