## **2. Statistical Analysis Plan**

Comparative statistics were completed between the control group and intervention groups using the student t-test. P-values <0.05 were considered statistically significant. Analyses were completed in RStudio (v1.2.1335).

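### The comfort and anxiety hypotheses (H2, H4) name no comparator or survey; only Survey B can test them by randomised arm, and only for anticipated outcomes

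*Combined protocol and SAP*

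**What the plan says.** Under Hypothesis and Objectives, the primary hypothesis (H1) is defined by randomised arm and has a stated comparator: "Subjects randomized to the intervention group will self-report increased understanding of their HS and management plan, as compared to the verbal consultation (VC").

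H2 and H4 are built differently. H2 states: "Subjects receiving a WAP will self-report increased comfort level in managing their HS at home with guidance from a WAP". The objective behind it concerns patients' "comfort level in following their individualized WAPs at home". H4 states: "Subjects receiving a WAP will self-report lower levels of anxiety in managing their HS at home". Neither says who the comparison group is, which survey supplies the answer, or when.

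Study Design and Procedures gives the sequence:

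- Survey A: "After group assignment, the study coordinator will administer Survey A which will take approximately 10 minutes to both groups". This is before the consultation.
- Consultation: "Next, the subjects in the control and intervention groups will receive an individualized VC and VC+WAP, respectively". Both groups then complete Survey B at the same visit.
- Controls only: "Those in the control group will then receive a VC+WAP, followed by completion of Survey C".
- Survey D: both groups, at a routine follow-up visit. The same section also says that intervention subjects have finished the study once Survey B is done.

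The Statistical Analysis Plan gives one test: "Comparative statistics were completed between the control group and intervention groups using the student t-test". It ties that test to no survey, item or hypothesis.

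**The concern.** After Survey B, a group defined by having received a WAP is the whole trial, because the controls have been given one too. A hypothesis worded by receipt then no longer picks out a randomised arm. The control-versus-intervention test can still be run at follow-up, but it no longer compares WAP with no WAP.

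Two wrong conclusions become possible. A null result at Survey D could be read as showing that the WAP does not help at home, when both arms hold one. A positive result at Survey B could be reported as greater comfort or less anxiety at home, when subjects have not left the clinic since the consultation. The plan does not say which survey decides, so the choice could be made after the results are seen.

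**Working it through.** The plan gives no sample size, effect size, standard deviation or allocation ratio, and no figure of its own on this point. The check is therefore one of design. A randomised test of the WAP's effect on experienced comfort or anxiety at home needs three things from one survey:

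(a) both randomised arms answer it;
(b) the arms differ in WAP receipt when they answer;
(c) subjects have spent time managing HS at home since the consultation.

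Reading the sequence in Study Design and Procedures against these:

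| Survey | WAP received: intervention | WAP received: control | (a) | (b) | (c) |
|---|---|---|---|---|---|
| A | 0% | 0% | yes | no | no |
| B | 100% | 0% | yes | yes | no |
| C | not surveyed | 100% | no | no | no |
| D | 100% | 100% | yes | no | yes |

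The percentages are the planned exposures and assume that subjects receive what the protocol assigns. The difference in receipt between arms is 100 − 0 = 100 percentage points at Survey B and 100 − 100 = 0 at Survey D. At Survey D the arms differ only in that controls had the VC alone first and received the WAP later in the same visit.

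No survey meets all three conditions. Survey B meets (a) and (b). It therefore supports a randomised comparison of how comfortable or anxious subjects expect to be.

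The two hypotheses then need separate treatment at Survey B.

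- **H4.** Its outcome is anxiety about managing HS at home, with no mention of using a WAP. Both arms can answer that in the same form. At Survey B the subjects who have received a WAP are exactly the intervention arm, so the control-versus-intervention test fits. Only the comparator, survey and time point are missing.
- **H2.** Its outcome includes guidance from a WAP, and its objective concerns following one. At Survey B controls have no WAP, so that question cannot be put to both arms in the same form. At Survey D both arms could answer it, but there is no arm without a WAP. As worded, H2 has no between-arm test at any survey. Without the reference to the WAP, it can be tested at Survey B like H4.

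Survey C allows at most a before-and-after comparison with Survey B within the control arm, which is not randomised.

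**The case against.** The strongest reply is that Survey B already supplies what is needed. Both arms complete it after different consultations and before controls receive the WAP, and patients can say how they feel about home management before leaving the clinic. This stands. A reader might infer that no survey gives a randomised comparison for these hypotheses; that is too strong, because Survey B does so for anticipated outcomes.

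It is also fair to say that H4 should not be bundled with H2. The argument about rating a WAP that one does not have applies to H2 only.

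A reader might further infer that the plan intends to group answers by WAP receipt, so that controls would count on both sides of a t-test. Nothing in the documents proposes this. The SAP compares the control and intervention groups. Nor can it be said that Survey B lacks suitable items, since the survey items are not in the text.

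Finally, the secondary objective could be descriptive among WAP recipients, or the increase could mean a change over time within subjects. The wording allows this, but the SAP names no within-group analysis. That reading would also give no evidence of WAP versus no WAP.

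What the reply does not remove is that the plan ties neither hypothesis to Survey B and does not rule out Survey D.

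**Conclusion.** The point holds in a limited form. H2 and H4 lack a comparator, survey and time point. Only Survey B gives a randomised contrast in WAP receipt (100 percentage points by design, against 0 at Survey D), and it bears on anticipated comfort and anxiety. A between-arm test at Survey D cannot show an effect, or a lack of effect, of the WAP at home. H2 alone also has an outcome that controls cannot rate in the same form at Survey B.

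This rests on subjects receiving the consultation assigned to them and on controls getting the WAP at the first visit as described. It does not depend on the allocation ratio. The effect on any estimate or on power cannot be calculated from the documents. The primary hypothesis is unaffected, so this is a change that should be made to the non-primary hypotheses; it is not a defect of the whole trial.

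**What to change.** 1. Define H2 and H4 as randomised intervention versus randomised control at Survey B, before controls receive the WAP.
2. Word H2 as expected comfort in managing HS at home, so that both arms can answer it. H4 needs no change to its outcome. State that both are anticipated outcomes.
3. Adjust each comparison for the subject's Survey A answer where the same item was asked, in place of the plain t-test. Note in the SAP that Survey A is taken after assignment but before the consultation.
4. Keep comfort in following the WAP as a descriptive result. Report Surveys C and D descriptively, and say that they are not evidence of WAP versus no WAP.
5. Reconcile the statement that intervention subjects finish at Survey B with their taking Survey D.

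No new visits or subjects are needed; the changes are to the wording of the objectives and to the SAP. The downside is a narrower claim, about anticipated and not experienced outcomes. The SAP is written in the past tense. If the analysis has already been done, apply these points as labels and limits in reporting, and mark the change to H2 and to the analysis as post hoc.

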### **Study Design and Procedures**

Patient recruitment will take place during a routine dermatology. If the HS patient meets the inclusion criteria, he/she will be approached by a study coordinator about this study. If he/she agrees, he/she will sign an informed consent form.

Subjects will then be randomized to one of two groups:

- A control group – VC alone
- An intervention group – VC with WAP

In order to randomize subjects, randomization lists, which are concealed to all parties involved in this study, will be created using a computer software program. As each subject is enrolled, they will be assigned a subject number. After assignment of a subject number, the investigators will refer to the computer-generated randomization scheme corresponding to the assigned subject number to complete the randomization process.

After group assignment, the study coordinator will administer Survey A which will take approximately 10 minutes to both groups. All subjects will be asked to refrain

from asking any questions regarding HS or its treatment until the end of the office visit to ensure controlled delivery of information to all subjects.

The principal investigator will then conduct a routine office visit for the HS patients, consisting of an introduction, history taking, and assignment of Hurley stage. Next, the subjects in the control and intervention groups will receive an individualized VC and VC+WAP, respectively. Subjects from both groups will then complete Survey B which will take approximately 10 minutes. At the completion of Survey B, subjects in the interventional group will have completed the study. Those in the control group will then receive a VC+WAP, followed by completion of Survey C which will take approximately 10 minutes. This is to ensure that all subjects receive the same caliber of care. All Surveys and WAP documents that will be used in our study of written action plans in hidradenitis suppurativa are a standard of care intervention.

Information collected into the medical record during the routine office visit (specifically duration of disease, tobacco use, and disease severity) will be used for this research.

Both groups will take Survey D at a routine follow up visit. Survey D (which will take approximately 10 minutes) is to evaluate if the action plan has had any long-term impact or if it results in behavior change.

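### Survey A, the only survey before the arms diverge, follows the look-up of the assignment with no masking described; completing it before randomisation would make it a true baseline at almost no cost

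*Combined protocol and SAP*

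**What the plan says.** Study Design and Procedures sets out one sequence. Consent is followed by randomisation, in which "the investigators will refer to the computer-generated randomization scheme corresponding to the assigned subject number to complete the randomization process". Then: "After group assignment, the study coordinator will administer Survey A which will take approximately 10 minutes to both groups". The principal investigator's routine visit comes next, "consisting of an introduction, history taking, and assignment of Hurley stage". Only after that do the arms diverge: "Next, the subjects in the control and intervention groups will receive an individualized VC and VC+WAP, respectively". Survey B follows.

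The one protective statement concerns the lists: "randomization lists, which are concealed to all parties involved in this study, will be created using a computer software program". The section does not say who is told the assignment once it has been looked up, or whether subject or coordinator is kept unaware. It does ask all subjects to save questions about HS until the visit ends.

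The Statistical Analysis Plan says: "Comparative statistics were completed between the control group and intervention groups using the student t-test". It does not say which survey's scores enter the test. Nowhere is Survey A called a baseline, and its content is not shown.

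**The concern.** A baseline measure is protected from allocation when it is completed before anyone concerned can know the allocation. Here the only candidate among the surveys is taken afterwards. The outcomes in Hypothesis and Objectives are self-reports of understanding, comfort, preference and anxiety, which knowledge of the arm could move. A subject who knows a written plan is coming might rate present understanding differently from one who knows it is not, and a coordinator who knows might present the survey differently.

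Hypothesis 1 speaks of increased understanding relative to verbal consultation. That can be read as a between-arm difference after the consultation or as a difference in change from Survey A. On the second reading, an allocation-related shift in Survey A goes straight into the treatment comparison. It could favour either arm, depending on which arm's answers moved and in which direction.

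**Working it through.** **Order of events.** Consent; look-up by the investigators; Survey A; history and Hurley stage; VC or VC+WAP; Survey B. Concealed lists limit foreknowledge of the next assignment. They do not describe masking after that subject's assignment has been read.

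**Conditions for bias through Survey A.** (a) The subject or coordinator knows the arm at Survey A. (b) That knowledge moves the answers. (c) Survey A enters a between-arm comparison. The documents settle none of the three.

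**Illustration.** The plan gives no sample size, SD, correlation or effect size, so there is no figure to reproduce and every input except the 0.05 level is assumed:

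- d = 0.2 SD, a rise in the WAP arm's Survey A from knowing the arm (higher = better)
- k = fraction of that rise which also appears in Survey B
- r = 0.5, correlation of Surveys A and B; unit SDs
- n = 50 per arm; no true effect; two-sided test (the plan does not state sidedness)

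Bias, WAP minus control:

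| Analysis | Present order | Survey A before randomisation |
|---|---|---|
| Survey B alone | k·d | k·d |
| Change score | (k − 1)·d | k·d |
| ANCOVA on Survey A | (k − r)·d | k·d |

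The standard error is SD × √(2/n), and √(2/50) = 0.200. The SDs are 1 for Survey B alone, √(2(1 − 0.5)) = 1 for the change score and √(1 − 0.25) = 0.866 for ANCOVA. The standard errors are therefore 0.200, 0.200 and 0.173. Bias divided by standard error is the noncentrality of the t statistic (98 degrees of freedom; 97 for ANCOVA).

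For the change score, the noncentrality at k = 0, 0.5 and 1 is −1.0, −0.5 and 0 in the present order, and 0, +0.5 and +1.0 after re-ordering. For ANCOVA it is −0.577, 0 and +0.577, then 0, +0.577 and +1.155.

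Two-sided type I error, present order → re-ordered:

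| k | Survey B alone | Change score | ANCOVA |
|---|---|---|---|
| 0 | 0.050 → 0.050 | 0.168 → 0.050 | 0.088 → 0.050 |
| 0.5 | 0.079 → 0.079 | 0.079 → 0.079 (sign reversed) | 0.050 → 0.088 |
| 1 | 0.168 → 0.168 | 0.050 → 0.168 | 0.088 → 0.208 |

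At k = 0 in the present order, the change-score error of 0.168 splits into 0.166 favouring control and 0.002 favouring WAP. A rise in the control arm's Survey A instead reverses every sign.

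**Range.** The present-order change-score figure at k = 0 is 0.107, 0.168 and 0.291 for 25, 50 and 100 per arm (r = 0.5), and 0.133 to 0.248 for r = 0.3 to 0.7 (50 per arm).

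**The case against.** The strongest reply is that the bias needs three undocumented links and that the plan's only named analysis may never touch Survey A. A t-test on Survey B alone is unaffected through Survey A. This stands, and it is why the point is conditional.

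Second, the re-ordering does not lower the error rate in every scenario. In the table it helps at zero carry-over, leaves the change score level at half carry-over and raises it at full carry-over; ANCOVA is worse after re-ordering at both half and full carry-over. This also stands as arithmetic. It is not a reason to keep the present order. Where that order does better, two biases cancel, and since carry-over cannot be observed nobody could verify or plan for the cancellation. What the table shows is that unmasked self-report at Survey B is a separate exposure which re-ordering does not touch.

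Third, Hurley stage is also assigned after the look-up, so a reader might infer that severity is compromised too. The documents do not support that. They do not say that the principal investigator does the look-up. Disease severity is to be used for the research, but no between-arm comparison, adjustment or subgroup is stated.

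A reader might also infer that the order shows failed allocation concealment at enrolment. It does not: consent comes before the look-up, and the issue here is measurement after assignment.

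**Conclusion.** The point holds as a conditional design weakness. The sequence and the absence of described masking are plain in the text; knowledge of the arm at Survey A, its effect on the answers and any between-arm use of Survey A are not. A reader might infer that the primary comparison is biased, or that moving Survey A would make it unbiased. Neither follows. The first needs all three links, and the second holds only if knowing the arm leaves Survey B unmoved.

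The error rates illustrate size and direction under assumed values for shift, carry-over, correlation and sample size; they are not estimates for this trial. The recommendation rests less on them than on the principle that a baseline should be fixed before allocation is known, and on the very low cost of doing so.

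**What to change.** **If enrolment is still open.** Complete Survey A after consent and before the randomisation scheme is consulted. This is a re-ordering within the same visit, using the same survey of about 10 minutes. The only downside is an occasional survey from someone who is not then randomised. State who knows the assignment at each step and whether the t-test uses Survey B scores or change from Survey A. State also that the re-ordering protects Survey A only.

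**If enrolment is complete**, as the past tense of the Statistical Analysis Plan suggests. Report the order actually followed, who knew the arm at Survey A and whether Survey A entered the t-test, and describe Survey A as a post-randomisation measure. The cost is a few sentences. Presenting results with and without Survey A would not show which is biased, because carry-over is not observable.

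**Optional.** Recording Hurley stage before the look-up is worth the small extra effort only if severity will be compared or adjusted for between arms.

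### The consultation shared by both arms is given after group assignment, and nothing stated prevents or records a difference by arm that is unrelated to the written action plan

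*Combined protocol and SAP*

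**What the plan says.** All of this is in section 1, Study Design and Procedures, unless noted.

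- **Assignment comes first.** The randomization lists are said to be concealed from everyone involved. Once a subject has a number, the investigators consult the scheme to complete randomization. Only then does the first survey take place: "After group assignment, the study coordinator will administer Survey A".
- **One stated control on information.** Subjects are to hold back "from asking any questions regarding HS or its treatment until the end of the office visit to ensure controlled delivery of information to all subjects".
- **Office visit.** "The principal investigator will then conduct a routine office visit for the HS patients", covering introduction, history and Hurley stage. After that, "the subjects in the control and intervention groups will receive an individualized VC and VC+WAP, respectively". The text does not say who gives the VC. The principal investigator is the natural reading.
- **Surveys after the consultation.** Survey B: "Subjects from both groups will then complete Survey B". Survey C: "Those in the control group will then receive a VC+WAP, followed by completion of Survey C". Survey D: "Both groups will take Survey D at a routine follow up visit".
- **Analysis.** Section 2 gives a Student t-test between the two groups. It names no survey and no adjustment.

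**The concern.** The primary objective (Hypothesis and Objectives) is the effect of adding the WAP. Comparing VC with VC+WAP isolates that effect only if the VC is otherwise the same in both arms. Randomization balances the patients. It does not balance what is done to them afterwards.

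Here the VC is tailored to each patient, and it is given when the arm has already been looked up. No script, topic list, duration or record of the VC is stated. Someone who knows that a control subject will have a VC+WAP straight after Survey B might keep the first consultation short. The same person might instead say more to make up for the missing document. Either habit would change the Survey B contrast for reasons unrelated to the WAP, and the planned test could not tell the two apart.

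**Working it through.** The documents give no sample size, standard deviation (SD) or effect size, so the plan has no figure to reproduce. The check is mainly a reading of the text.

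**Step 1: order of events.** Consent; subject number; lookup of the arm; Survey A; history and Hurley staging; VC or VC+WAP; Survey B. For controls, a VC+WAP and Survey C follow. Survey D comes at a later visit for both groups. The arm is therefore available before any consultation content is delivered.

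**Step 2: does anything stated keep the VC equal by arm?**

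| Feature in the text | What it does | Does it equalize the VC by arm? |
|---|---|---|
| Concealed lists | Hides the upcoming sequence | No; the arm is known to whoever looks it up |
| Subjects hold questions | Limits what patients prompt | Only in part; it does not limit what the consulter says |
| Principal investigator conducts the visit in both arms | Limits differences between providers, if that role also gives the VC | No; one person can consult differently by arm |
| Controls later receive VC+WAP, so that care is equal | Equalizes care after Survey B | No; it acts after the comparison |

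**Step 3: which survey carries the comparison?** Survey A precedes the VC, so it cannot adjust for VC differences. Survey C is taken by controls only, after a VC+WAP. By Survey D, controls have also had a WAP. Survey B is the one remaining survey that compares VC with VC+WAP after the consultation. This is inferred from the visit order, because section 2 names no survey.

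**Step 4: what the estimate contains.** Let W be the effect on Survey B of the WAP, including the talk needed to review it. Let b be the effect on Survey B of any other difference by arm in the VC. Then

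expected difference in Survey B = W + b.

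The t-test estimates the sum. A larger sample narrows the interval around W + b and does not bring it closer to W.

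**Step 5: generic illustration, all inputs assumed.** Take a two-sided 0.05 t-test, n per arm, and b in SD units of the survey score. The 95% interval misses W with the probability that a noncentral t with parameter b × √(n/2) and 2n − 2 degrees of freedom exceeds the critical value in either tail. For b = 0.2 the parameter is 0.2 × √15 = 0.775 at n = 30, and 0.2 × √25 = 1.0 at n = 50.

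| Assumed b | Coverage, n = 30 | Coverage, n = 50 |
|---|---|---|
| 0 | 95% | 95% |
| 0.1 SD | 1 − 0.0668 = 93.3% | 1 − 0.0785 = 92.1% |
| 0.2 SD | 1 − 0.1187 = 88.1% | 1 − 0.1677 = 83.2% |
| 0.3 SD | 1 − 0.2079 = 79.2% | 1 − 0.3178 = 68.2% |

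The same pattern would appear in any two-arm trial with a shift of this size. The table shows only that more subjects do not cure the problem. It says nothing about how large b is here, and the priority of this point does not rest on it.

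**The case against.** The strongest reply is that the harm is hypothetical. Any trial in which an unmasked clinician delivers an add-on carries this risk, and the documents show no sign that the VC differed. That stands, and it limits the weight of the point.

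Second, the intervention arm is defined as "An intervention group – VC with WAP". If going through an individualized plan changes the conversation, that change is part of what a clinic would adopt. This also stands. Talk that belongs to reviewing the WAP is not contamination, and the concern is confined to VC differences unrelated to it.

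Third, the plan has some protection: one role conducts the visit in both arms, and patients hold their questions. Both help. Neither acts on how the same person consults in one arm compared with the other.

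Fourth, the person handing over the WAP cannot be masked to it. That is true, but the VC can be standardized and recorded and, where the two are separable, given before the arm is released.

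A reader might go further and infer that allocation concealment failed, or that the VC was in fact shorter for controls and so favoured the WAP. The documents support neither. The lists are stated to be concealed, and nothing is said about how the VC was actually delivered.

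**Conclusion.** The point holds in limited form. The plan neither prevents nor records a difference by arm in the shared VC that is unrelated to the WAP. If one arose, its effect would be added in full to the Survey B estimate.

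The size and direction are unknown and cannot be derived from the documents. The conclusion rests on two readings: that Survey B carries the randomized comparison, and that the person giving the VC can know the arm. The text does not say outright that this person looks it up, but the investigators do the lookup and nothing keeps the result from the consulter.

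It would be too strong to read this as evidence that the result is biased, or to treat every verbal difference between arms as contamination. This is a lower-priority point, worth acting on because the remedy is cheap.

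**What to change.** 1. Keep the same scheme, but move the lookup to after Survey A, history, Hurley staging and the common VC. The WAP is then reviewed before Survey B in the intervention arm and after Survey B in the control arm.
2. Use one VC topic checklist in both arms with the minutes recorded. Record WAP-review minutes separately, and report both by arm.
3. If the VC and WAP must be delivered together, release the assignment after Survey A and staging. That protects those baseline measures only, so the checklist has to do the work for the VC.
4. Section 2 is written in the past tense. If enrolment has ended, report how the VC was delivered in each arm, as far as it is known, and state the limitation.

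**Cost.** A one-page checklist and a later lookup within the same visit, with no added staff or visits; under item 4, a sentence or two of reporting.

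**Downsides.** Under item 1 the tested intervention becomes VC followed by WAP review, not a combined delivery. The contact time of that review stays in the contrast; recording the minutes shows it but does not remove it. The checklist documents differences and may reduce them, but it does not mask the consulter. Under every option, subjects know at Survey B whether they have received a WAP, so expectation bias in self-report remains.

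### By Survey D both arms have received the written action plan, so no comparison there can show its long-term effect, and the SAP names no Survey D analysis

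*Combined protocol and SAP*

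**What the plan says.** The protocol, under Study Design and Procedures, sets out this sequence.

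- At the index visit, "the subjects in the control and intervention groups will receive an individualized VC and VC+WAP, respectively" (VC is the verbal consultation). Both groups then complete Survey B.
- "Those in the control group will then receive a VC+WAP, followed by completion of Survey C". The reason given is "This is to ensure that all subjects receive the same caliber of care".
- For the other arm, "At the completion of Survey B, subjects in the interventional group will have completed the study".
- Later, "Both groups will take Survey D at a routine follow up visit". The interval is not given. Survey D "is to evaluate if the action plan has had any long-term impact or if it results in behavior change".

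The Statistical Analysis Plan has one analysis: "Comparative statistics were completed between the control group and intervention groups using the student t-test", with "P-values <0.05 were considered statistically significant". It names no survey, outcome, time point or within-patient analysis. The four hypotheses in Hypothesis and Objectives name no survey, and none mentions long-term impact or behaviour change.

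**The concern.** The aim given to Survey D is a question about what the WAP does over time. Answering it needs a group without a WAP, or at least an analysis that does not depend on one. The design removes the first at the index visit and the SAP does not supply the second.

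Two misreadings are possible. A null at Survey D could be reported as no lasting effect, although both arms may have gained equally. A difference could be reported as a WAP benefit or harm, although it may come from the controls' second consultation.

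The completion wording adds a further doubt: read literally, the intervention arm leaves the study before Survey D, and follow-up data would then exist for controls only.

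**Working it through.** The documents give no sample size, effect size or SD, so there is no planned figure to reproduce. The main check is an account of exposure, which needs no assumed number.

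**Exposure at each survey, from Study Design and Procedures**

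| Survey | Control arm has had | Intervention arm has had | WAP-free group? |
|---|---|---|---|
| B | VC | VC+WAP | Yes |
| C | VC, then VC+WAP | not taken | No |
| D | VC, then VC+WAP (and Survey C) | VC+WAP | No |

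**Expected difference at Survey D.** Let *w* be the lasting WAP effect, *v* the effect of the controls' extra consultation, and *r* the share of the WAP effect that controls obtain, all in SD units. Intervention minus control is

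*d* = *w* − (*r·w* + *v*).

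With *r* = 1 this is *w* − *w* − *v* = −*v*, so *w* drops out. At Survey B the corresponding difference is *w*.

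**Illustration.** Alpha of 0.05 is from the SAP. Everything else is assumed: two-sided test, SD 1, and the values of *n* per arm, *w*, *v* and *r*. The method is the two-sample t-test with 2*n* − 2 degrees of freedom and noncentrality *d*·√(*n*/2). For *d* = 0.2 and *n* = 50, noncentrality is 0.2 × √25 = 1.0 and the rejection rate is 16.8%.

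Rejection rate at 50 per arm, *r* = 1:

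| True WAP effect *w* | Survey B | Survey D, *v* = 0 | Survey D, *v* = 0.2 |
|---|---|---|---|
| 0 | 5.0% | 5.0% | 16.8% |
| 0.2 | 16.8% | 5.0% | 16.8% |
| 0.5 | 69.7% | 5.0% | 16.8% |
| 0.8 | 97.7% | 5.0% | 16.8% |

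- The Survey D columns do not change with *w*. Simulation (40,000 runs, *w* = 0, 0.5 and 0.8) gives 5.1%, 4.9% and 4.9% with *v* = 0, and 16.7%, 16.6% and 16.9% with *v* = 0.2.
- With *v* = 0.2, the rate is 11.9% at 30 per arm and 29.1% at 100. At 50 per arm, 16.6 of the 16.8 percentage points favour control, which follows from taking *v* as positive.
- A separate simulation (20,000 runs) with *v* = 0.3 rejects in about 15% of runs at 20 per arm and 32% at 50, including when *w* = 0.

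**If controls gain less from a later WAP.** Take *r* = 0.8 and *w* = 0.5. With *v* = 0, *d* = 0.5 − 0.4 = +0.10. With *v* = 0.2, *d* = 0.5 − (0.4 + 0.2) = −0.10. Either way the test rejects 7.9% of the time at 50 per arm. The same WAP effect can give either sign.

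**Completion wording.** One sentence has intervention subjects finished at Survey B; a later one in the same section has both groups take Survey D. As written they cannot both be true.

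**The case against.** The strongest reply is that the protocol never says Survey D will be compared between arms. With everyone WAP-exposed, it can be read as follow-up of a single cohort, perhaps asking whether patients used their plan, and the survey items are not in the documents. That reading is fair, but it leaves an evaluative aim about the WAP with no WAP-free group and no stated analysis.

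Other points have some force:

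- The crossover is deliberate and serves equal care. That stands, and nothing here asks for its removal. It does not make the later comparison interpretable.
- The SAP assigns no survey to any analysis, so the missing Survey D analysis is one instance of a wider gap. That also stands; on its own it would be a minor point.
- Hypotheses 2 and 4 concern managing the disease at home, and Survey D is the only survey clearly placed after patients have gone home with a plan. It cannot be ruled out that Survey D was meant to serve them. If it was, the loss of the comparator matters more, not less.
- The completion sentence probably means the index visit only. That is the likely reading, but the text does not say so.
- The numerical illustration rests on chosen inputs. It does; the conclusion rests on the exposure sequence.

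**Conclusion.** The concern holds. As planned, Survey D has no WAP-free comparator, so its stated aim goes beyond what the design can show. Under an equal, additive WAP effect in both arms, a between-arm test at Survey D carries no information about that effect, whatever its size. If the effect is unequal, the result mixes the WAP with the controls' extra consultation, and even its sign is not decisive. The exposure sequence is certain from the text; the rejection rates are illustrative only.

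The problem is limited to Survey D. The randomised contrast at Survey B, VC against VC+WAP, is intact and can serve Hypothesis 1. What is at risk is any long-term or behaviour-change conclusion. This should be fixed, but it does not damage the primary comparison.

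**What to change.** 1. In the SAP, name Survey B as the only randomised WAP versus no-WAP comparison, and restrict the between-arm t-test of the WAP to it.
2. Reword the Survey D aim, for example: *to describe durability of understanding and self-reported behaviour in patients who have all received a WAP*.
3. Where Survey D shares items and scales with an earlier survey, report paired within-patient change with 95% CI by arm, labelled descriptive and uncontrolled. Where it does not, report Survey D summaries with 95% CI only.
4. State that neither a difference nor a null between arms at Survey D will be taken as presence or absence of a WAP effect.
5. Reconcile the sentence ending the intervention arm's study at Survey B with the one giving Survey D to both groups, and report how many in each arm complete Survey D.

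The cost is wording in both parts of the document and descriptive summaries of a survey already planned; no new visits or patients are needed. The paired analysis depends on shared items, which the documents do not show. The trial gives up a causal long-term claim. The SAP is written in the past tense, so if analysis has already been done, the change should be dated and disclosed as made afterwards.
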